1. STUDY OBJECTIVES

1.1 Primary Objective

The primary outcome will be self-reported tobacco abstinence. We will measure 7-day point prevalence, 30-day point prevalence and prolonged abstinence at the 6-month follow-up assessment. All participants who report abstinence at the 6 month assessment and agree to perform a saliva test will be biochemically validated. We hypothesize that participants in the Imagery Intervention Condition will report equal or higher rates of cessation than those in the Control Condition.

Our feasibility outcomes include: at least 50% of participants will complete the 6-session intervention program; 50% Of the IIC participants will report listening to the guided imagery audio files at least 5 times per week; 50% will visit the website at least one time; and 75% of participants will complete both follow-up assessments.

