1.2 Secondary Objectives

Secondary outcomes will include reduced tobacco use (for non-quitters), increased self-efficacy for quitting, and reduced nicotine cravings. We hypothesize that participants in the Imagery Intervention Condition will report equal or lower levels of tobacco use and cravings, and equal or higher levels of self-efficacy for quitting.

In addition, we will explore the demographics of study participants to assess how they may differ from the general population of ASHLine callers.

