Guided imagery is a mind-body technique that involves the visualization of mental images and is similar to mindfulness meditation (MM). Both mindfulness meditation and mental imagery can create awareness and direct attention to one's thoughts, feelings, and health behaviors. Guided imagery and other mindfulness interventions can effectively assist tobacco users to quit (Brewer et al., 2011; Wynd, 2005; Zernig et al., 2008). One randomized controlled trial with 779 adult smokers compared the use of bupropion with brief psychotherapy that was taught to participants over 2 days lasting 8 hours (Zernig et al., 2008). The latter condition consisted of exposure to guided imagery intended to enhance self-management, decidedness, assertiveness, selfdetermination, and self-assurance. Intent-to-treat analysis showed 12-month abstinence rates of 39.1% and 12.3% for the psychotherapy and bupropion groups, respectively. These rates were 39.9% (psychotherapy) and 22.5% (bupropion) for those who completed the study. In another four week randomized controlled trial, 33 adults were taught mindfulness and encouraged to practice at home (Elwafi et al., 2013). Results showed that home practice predicted reduced cigarette use, and informal mindfulness practice moderated the relationship between craving and cigarette use (Elwafi et al., 2013). Another smaller trial compared those receiving education and counseling with education/counseling plus imagery training (Wynd, 2005). Results of that study indicated abstinence rates of 12% and 26%, respectively (Wynd, 2005). These studies support the efficacy of guided mental imagery for smoking cessation.

However, these studies employed in-person interventions that are prohibitively expensive and limit larger scale implementation and overall reach. Combining the use of guided imagery with tobacco QL services offer a highly scalable, innovative, and a cost-effective strategy for delivering a guided imagery intervention. We will develop, using input from expert consultants, a community advisory board, and our target population, a guided imagery intervention, attention-control condition, and recruitment strategies. The intervention has little potential risk and may increase the use of telephone-based tobacco cessation counseling by male and racially-/ethnically-diverse smokers.

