Website Use								Х	х
Imagery File Use								Х	х
Imagery Vividness								Х	Х
Consumer Satisfaction								х	х
Treatment Administration Form		х	Х	Х	х	Х	х		
Concomitant Medications	Х	х	Х	Х	х	Х	Х	Х	х
Adverse Events		х	Х	Х	х	Х	Х		

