9.3 Definition of Populations

We will be using maximum likelihood based mixed models for all outcomes measured over time, using all available data. Mixed models are consistent with an intention to treat analysis due to their implicit imputation of missing data.

(Molenberghs et al., 2004). The per protocol population is defined as users who complete the 6-session intervention session.

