9.5.3 Process and Exploratory Outcomes (Intervention Condition Participants)

All Participants

Website use. We collect usage data and can analyze use of all components of the site. Data most likely related to outcome will include, but not be limited to: (a) the length of time participants interact with the site; (b) the number of pages they visit within the site, and (c) the number of links they click on while using the site.

System usability. At both follow-up assessments, we will use Tullis and Stetson's (2008) 10-item adaptation of Brooke's widely used System Usability Scale (Brooke, 1996) to rate the usability of our website.

Imagery files use. These data will be collected automatically by the website. We will collect number of times and which imagery files were listened to completely, and if the participant created their own file.

Website use. We collect usage data and can analyze use of all components of the site. Data most likely related to outcome will include, but not be limited to: (a) the length of time participants interact with the site; (b) the number of pages they visit within the site, and (c) the number of links they click on while using

the site.

Imagery Intervention Condition Participants Only

Imagery files use. We will collect number of times and which imagery files were listened to completely, and if the participant modified and/or created their own file.

Imagery mastery. Ratings of imagery vividness and controllability will be measured weekly via the website in order to verify compliance with the protocol (Marks, 1973).

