9.6 Data Analyses

Feasibility outcomes, including recruitment and dropout, will be described using frequencies and percentages, and 95% confidence intervals. Questionnaires will be scored according to developer instructions. Tobacco use outcome measures will use appropriate mixed models (linear for continuous outcomes and generalized linear with a logistic link for binary) using time categorically. Comparisons between the intervention and control group at 8 weeks and 6 months will be carried out using contrasts within these models. Mixed models are robust to missing outcome data (including dropout) and model misspecification, and are consistent with an intention to treat analysis (Bell and Fairclough, 2014; Mallinckrodt et al., 2004; Molenberghs et al., 2004). Mixed models will also be used to model self-efficacy, cravings, and consumer satisfaction, and to estimate intervention effects. Outcomes measured in the intervention group (e.g., imagery file use, website use), appropriate descriptive statistics will be computed, including means, standard deviations, ranges and frequencies/proportions. Linear regression and chi-square tests of trend will be used to assess the stability of the system usability and website/file use over time. We are underpowered to detect any subgroup analyses, but will conduct exploratory analyses in anticipation of the larger trial by including appropriate interactions within the mixed models. We will compare guided imagery use with tobacco outcome measures using linear regression in order to investigate a "dose-response" effect of the intervention. Demographics will be described with means, standard deviations, ranges and frequencies/proportions and will be explored as correlates for successful tobacco outcomes.

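### Minor: the stability tests for usability and website/file use, as ordinarily applied, ignore repeats on the same person and conflict with section 9.3; the role of baseline in the secondary models is also unstated

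*Combined protocol and SAP*

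**What the plan says.** Section 9.3 sets a general rule: "We will be using maximum likelihood based mixed models for all outcomes measured over time, using all available data". Section 9.6 follows it for tobacco use, self-efficacy, cravings and consumer satisfaction, then departs from it for the process measures: "Linear regression and chi-square tests of trend will be used to assess the stability of the system usability and website/file use over time".

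These measures are repeated within person. Section 9.5.3 has "System usability. At both follow-up assessments, we will use" followed by the scale, and section 6.2.2 agrees. Website use is logged automatically (section 6.2). Table 3 in section 6 puts the rows for website use and "Imagery File Use" at both follow-ups, whereas Table 4 in section 6.2.2 marks both as daily. For these outcomes no section names a paired test, a per-person summary, GEE or a clustered standard error. The heading of section 9.5.3 classes them as process and exploratory.

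On baseline, section 9.6 makes time categorical in the tobacco-use models and adds: "Comparisons between the intervention and control group at 8 weeks and 6 months will be carried out using contrasts within these models". Tables 3 and 4 show dependence, cravings, self-efficacy and tobacco use measured at baseline. No section says whether baseline is a covariate, a level of the time factor (with or without equal arm means), the reference for a change score, or left out.

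**The concern.** (a) Whether something is stable over time is a question about change within people. An ordinary regression on time, or an ordinary chi-square trend test, computes its error as if every record came from a different person. The intervals and p-values for change are then wrong. With two usability ratings that correlate positively, the interval is too wide, so a real change is more likely to be reported as stability. Section 9.1 says the study should show whether procedures work and whether the measures are right, and a trend in usability or engagement bears on that.

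(b) If baseline is simply a free level of time, the 6-month contrast gains almost nothing from it. The contrast is still valid, but the intervals for dependence, cravings, self-efficacy and cigarettes smoked could be wider than the collected data require.

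**Working it through.** **The plan's nearest figure.** The plan gives no number for the stability tests or for baseline. Section 9.2.1 claims 80% power at 0.7 SD with 50 per group, 20% dropout and a two-sample t-test. At 50 × 0.8 = 40 per arm, the noncentral t gives 87% power, and the effect detectable with 80% power is 0.634 SD. The stated power is therefore conservative, and nothing below depends on it.

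All correlations, variances and time grids below are assumptions, because the documents give none.

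**Usability, two ratings (SD units).** With n people rating twice at correlation ρ:
- ordinary SE = √(2/n)
- correct SE = √(2(1−ρ)/n)
- ratio = 1/√(1−ρ) = 1.20, 1.41, 1.83 at ρ = 0.3, 0.5, 0.7

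A nominal 5% test then has a true size of about 1.9%, 0.6% and 0.03%.

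The number of raters comes from the targets in section 1.1: "50% will visit the website at least one time; and 75% of participants will complete both follow-up assessments". If 75% of 120 = 90 people rate twice, the ordinary 95% half-width is 1.96 × √(2/90) = 0.29 SD, against 0.24, 0.21 and 0.16 SD paired. The chance of detecting a true change of 0.2 SD is 23%, 19% and 13%, against 36%, 48% and 69% paired. If only the half who open the site can rate it (45 people), the half-width is 0.41 SD, against 0.35, 0.29 and 0.23 SD.

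**Usage, T equally spaced time points.** Let t run from −0.5 to 0.5, with Sxx the sum of t². Take intercept variance 0.5, residual variance 0.5, and personal slopes with end-to-end SD k:
- ordinary variance of the slope = (1 + k²·mean(t²))/(n·Sxx)
- true variance = (k² + 0.5/Sxx)/n

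n cancels in the ratio. Example for T = 6 and k = 1: Sxx = 0.70 and mean(t²) = 0.117, so n times the ordinary variance is 1.117/0.70 = 1.595 and n times the true variance is 1 + 0.714 = 1.714. The SE ratio is √(1.595/1.714) = 0.96, and the true size is 5.9%.

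True size of the nominal 5% regression test:

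| Time points | k = 0 | k = 0.5 | k = 1.0 |
|---|---|---|---|
| 2 | 0.6% | 1.1% | 2.8% |
| 6 | 0.6% | 1.6% | 5.9% |
| 24 | 0.6% | 5.2% | 21% |

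A mixed model with only a random intercept gives 5%, 8% and 15% at 6 points, and 5%, 17% and 36% at 24, so it is not a cure. In simulation at 6 points, person-level slopes held about 5% throughout.

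A separate simulation (50 people, 6 weekly values, correlation 0.3, 0.5, 0.7) shows the same reversal. With no difference in personal trends, the size was 2.4%, 1.0% and 0.03% for regression and 3.5%, 1.8% and 0.7% for the chi-square trend test. With an assumed slope SD of 0.3 per week, it was 14%, 12% and 10% for regression and about 10%, 9% and 8% for chi-square.

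**Baseline.** Take 50 baselines and 40 six-month values per arm, dropout at random, 8-week data ignored, and baseline correlation r = 0.3, 0.5, 0.7.
- Free time level: the variance of an arm's 6-month mean is σ²[(1−r²)/40 + r²/50] = (σ²/40)(1 − 0.2r²). The detectable effect is 0.634 × √(1 − 0.2r²) = 0.63, 0.62, 0.60 SD.
- Baseline as covariate: 0.634 × √(1−r²) = 0.61, 0.55, 0.45 SD.
- Change score at 40 per arm: 0.634 × √(2(1−r)) = 0.75, 0.63, 0.49 SD, which is worse than ignoring baseline when r is below 0.5.

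**The case against.** Section 9.6 does not say that person-by-time records will be pooled. Linear regression could mean one summary per person or clustered errors, and the preceding sentence in 9.6 assigns descriptive statistics to file and website use. That is why the point is limited to the tests as ordinarily applied. The conflict with section 9.3 remains, and one sentence would settle it under either reading.

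The usage figures have no fixed direction and rest on assumed grids and variances. That is correct. A reader might infer that the plan always leans towards stability, or always towards false trends. The documents support neither for usage, since they do not say how far personal trends differ. Only the two-occasion usability result has a clear direction.

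A reader might also infer that the feasibility criteria or the cessation result are compromised. They are not. The website criterion is a single proportion (ever used), not a trend test, and the arm contrasts come from mixed models.

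On baseline, the fair objection is that this is preference, not error. Categorical time with baseline as a level is a natural reading and gives a valid contrast. Missing baseline adjustment should not be read as bias. The planned likelihood model also recovers a little information from baselines of dropouts, which is why the comparator above is 0.63, 0.62 and 0.60 SD rather than 0.634 throughout.

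**Conclusion.** (a) holds as a minor inconsistency. The stated method for usability and website/file use conflicts with section 9.3 and, as ordinarily applied, misstates the uncertainty of change. For usability the SE is too large by 1.20 to 1.83 over assumed correlations of 0.3 to 0.7. For usage the size and direction of the error are unknown: 0.6% to 21% for a nominal 5% test over the scenarios tabulated. No threshold or go/no-go rule depends on these tests.

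(b) is an optional gain in precision. The detectable effect falls by about 0.02 SD at r = 0.3 (0.629 to 0.605) and 0.15 SD at r = 0.7 (0.602 to 0.453), given dropout at random and no use of 8-week data. It does not apply to consumer satisfaction, which has no baseline.

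**What to change.** Replace the sentence in section 9.6. For the two usability ratings, specify a paired analysis or a mixed model. For website and file use, specify a participant-level analysis that allows personal trends to differ: person-level slopes or change scores, participant-clustered standard errors or GEE, or a mixed model with random slopes, not a random intercept alone. Person-level slopes and clustered errors avoid convergence trouble with sparse, zero-heavy usage data. Report each change with a 95% CI and state the time unit, since Tables 3 and 4 differ.

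Optionally add one sentence: baseline enters the models for dependence, cravings, self-efficacy and cigarettes smoked as a covariate. Constraining the arms to a common baseline mean is an equivalent option only when all randomised participants are analysed. It must not be imposed on cigarettes smoked among non-quitters. Section 1.2 restricts that outcome ("Secondary outcomes will include reduced tobacco use (for non-quitters), increased self-efficacy for quitting, and reduced nicotine cravings"), and the group is formed after randomisation, so its baseline means need not be equal between arms.

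The cost is one replaced and one added sentence, with no new data and no design change.

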10. DATA COLLECTION AND QUALITY ASSURANCE

10.1 Data Collection Forms

All baseline data collection will take place over the telephone by ASHLine staff who will be blinded to the participants' allocation to the intervention or control groups or by study staff. All data will be collected within the ASHLine 2.0 system and/or the REDCap system, which follows HIPAA standards for privacy and security. The study website will be integrated with the ASHLine 2.0 system and will also be HIPAA compliant. Follow-up assessments will be collected online and stored via REDCap on our secure servers. Data from follow-up assessments conducted on the

phone by study staff will be entered directly into the REDCap system on our secure server.

10.2 Data Management

Data and Safety Monitoring Plan

Based upon the NIH definitions of clinical trials, this is not a Phase III clinical trial, therefore, no data and safety monitoring board is required. Only a data and safety monitoring plan is required.

Entities conducting monitoring of the study:

The Human Subjects Committee (institutional Review Board [IRB]) at the University of Arizona (UA) will review and provide oversight for the proposed research.

What is monitored:

Once approved by the UA IRB, the following aspects of the study and study conduct are monitored: all procedures to ensure conformity with the approved study protocol; unforeseen circumstance that might arise and affect participant safety; all reports of serious adverse events and defined in 38 CFR 46 (death, new or prolonged hospitalization, persistent or significant disability or incapacity; congenital anomaly or birth defect); Other significant adverse events that lead to participant dropout, participant termination by the principal investigators, or termination of participation in the intervention.

Data Monitoring

Data handling and quality

Assessments will be administered to study participants as described in E1. All aspects of data collection and data storage will be carefully monitored to ensure rapid detection or errors, inconsistencies or other problems. Study personnel involved in data collection will follow a strict written protocol that describes study measures for protecting data privacy, clearly explains to study participant that she has the right to refuse to participate or refuse to answer any individual question that she wishes to not answer, and emphasizes reporting as accurately and truthfully as possible. The Principal Investigator and co-Investigators are experienced in training study staff in handling sensitive and confidential data, and in the storage and processing of such data.

No survey data resides on the website. It is used solely as a collection and submission device through a broadband internet connection to the University of Arizona Computer Science data center. The transmission of survey data between the web and database server where it is stored, is encrypted via a 128-bit SSL certificate.

Physical access to the data center is restricted to authorized personnel. All servers are housed in a locked rack and secured from the Internet and other university departments through the use of a hardware-based firewall and virtual LAN. A host-based firewall is installed and configured on each server as a secondary level of defense from outside intrusion. All servers and computer systems on the network are

configured with domain-managed accounts and password controls with audit logs. Access to server resources such as project data are restricted to authorized users only as approved by the project's Principal Investigator.

All servers and data are backed up daily to disc and tape with secure offsite storage at the University of Arizona's Computer Center.

Safety monitoring plan

Population: The proposed study involves smokers who want to quit tobacco. Since the study intervention is empirically based, and all participants are interested in quitting, it is unlikely that completing assessments or interacting with the website will cause an "adverse event" among the study populations. However, quitting smoking can cause discomfort, with physical symptoms and changes in mood.

Adverse events: We will use the definition of adverse events in the NIH OHRP document "Guidance on Reviewing and Reporting Unanticipated Problems Involving Risks to Subjects or Others and Adverse Events."

Adverse event (AE): Any untoward or unfavorable medical occurrence in a human subject, including any abnormal sign (for example, abnormal physical exam or laboratory finding), symptom, or disease, temporally associated with the subject's participation in the research, whether or not considered related to the subject's participation in the research

Serious adverse event: Any adverse event that: (1) results in death; (2) is life-threatening (places the subject at immediate risk of death from the event as it occurred); (3) results in inpatient hospitalization or prolongation of existing hospitalization; (4) results in a persistent or significant disability/incapacity; (5) results in a congenital anomaly/birth defect; or (6) based upon appropriate medical judgment, may jeopardize the subject's health and may require medical or surgical intervention to prevent one of the other outcomes listed in this definition.

It is possible that some questions about personal behaviors (e.g. smoking) might cause emotional discomfort to participants. Care will be taken to ensure that all participants understand that they may choose not to answer any question. Quitting smoking may result in physical symptoms (e.g., sleep disturbance) and changes in mood (e.g., irritability). Participants will be queried about AEs at each phone contact by coaches, and participants will be given a study telephone number to contact the study staff if they have any concerns about an untoward medical event.

Reporting: It is highly unlikely that any of the study procedures will cause an AE or SAE. Should an AE or SAE occur, ASHLine personnel and research study staff are trained to immediately report AEs connected to implementation of the intervention to [name] (co-I) or [name] (PI) who will keep a log of AEs and SAEs. In the event of an SAE, we will file a report with the University of Arizona (UA) IRB. As part of this process the UA IRB will determine if the event is directly related to project

procedures, so that It can be determined if project procedures should be modified. Information about all AEs and SAEs will be provided in annual progress reports to UA IRB and NCI.

10.3 Quality Assurance

10.3.1 Training

All ASHLine and study staff will complete CITI training in the protection of human subjects and responsible conduct of research prior to engaging in any study-related activities. ASHLine personnel who will describe the study, screen, and enroll participants will be trained by [name] and [name], who will ensure that these staff demonstrate understanding and proficiency in all tasks prior to implementation. Project coaches will be trained by Drs. [name] and [name] on the use and administration of either the guided imagery intervention or the attention-control protocol. [name] has previously developed and applied theory-based principles for training individuals to use and train others to administer guided imagery for behavior change. This included readings about the use of guided imagery and role playing exercise. These training sessions will occur in person and over ongoing/weekly telephone conversations prior to the implementation of the feasibility trial. Similar training (e.g., method, duration, etc.) will occur for coaches in both conditions.

